#### **Primary outcome variable(s)**

PRIMARY OUTCOME: Treatment of clinically suspected UTI within three weeks of surgery. This is defined as any symptomatic UTI requiring treatment with antibiotics as determined by the development of 2 or more of the following symptoms, in the absence of vaginal symptoms: urinary frequency; urinary urgency; dysuria; fever over 38°C/100.4°F; suprapubic, flank, or back pain; and/or chills. Patients will be encouraged to undergo urine culture prior to empiric treatment, but a positive urine culture will not be required as part of the primary outcome. We feel that this more accurately reflects the diagnosis and treatment of UTI in the clinical setting as: 1) it may not always be possible to delay treatment until patients are able to undergo urine culture; 2) accuracy of self-reported symptoms for the diagnosis of UTI is high; 3) the probability of UTI in patients with combinations of symptoms is very high.

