#### **Secondary outcome variable(s)**

SECONDARY OUTCOME: - cost-effectiveness of prophylaxis with methenamine hippurate for prevention of post-operative UTI compared to prophylaxis with fluoroquinolones - rate of culture-positive symptomatic UTI - prevalence of antibiotic resistance in positive post-operative cultures - prevalence of side effects following a 24-hour course of methenamine hippurate - factors that may influence patient compliance with short-course of chemoprophylaxis. Cost-effectiveness data: We plan to perform a cost-effectiveness analysis from a societal perspective, which will be expressed as incremental cost per UTI prevented. Routine costs of prevention of UTI with methenamine hippurate prophylaxis will be compared with costs of prevention of UTI with fluoroquinolone prophylaxis. We plan to capture incremental direct health care costs, which will be estimated using the resource costing method. Direct medical service standard of care use (such as number and types of physician visits, hospital admissions lengths, emergency transport and emergency room visits), and direct medical costs (such as antibiotic treatment of UTI, prophylaxis with methenamine or ciprofloxacin, urine laboratory tests, or treatment of complications like pyelonephritis) will be monetized by multiplying the number of units of each resource used per treatment arm by the average unit cost of these items in dollars. Detailed individual cost data will not be collected. This method allows a consistent capture of resource use when costs are incurred across multiple health systems or payers. Cost for each direct medical service use, direct non-medical items, and indirect items will be assigned based on national Medicare reimbursement rates or other standardized unit costs. Among patients who undergo urine culture as part of standard of care for UTI, the rate of positive cultures will be identified. As per standard of care, antibiotic resistance will be collected by sensitivity testing on all positive urine cultures identified from samples collected for evaluation of symptomatic UTI in post-operative patients. Bacterial species and sensitivities will be identified and recorded. To determine medication compliance rates, any unused medication will be returned to the office at their post-operative follow-up visit. As per routine care, investigators will also ask patients during the weekly routine post-operative call and routine post-operative visits about their compliance with the second dose of medication. Adverse effects from the administration of methenamine and fluoroquinolones will be collected. Patients will be asked to document any side effects, including nausea, vomiting, pruritis, and rash, that may occur within 24 hours of the administration of the last dose of methenamine or antibiotic.

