**Procedures**

**RECRUITMENT** We plan to recruit women from 3 clinical sites associated with 3 departments in the University of Pennsylvania Health System: 1) Urogynecology at Hospital of University of Pennsylvania (HUP), 2) Urogynecology at Pennsylvania Hospital (PAH) and 3) Urology at Pennsylvania Hospital (PAH). Physician investigators, who are present at all sites, will screen patients planning for surgery for pelvic organ prolapse, urinary incontinence, or both, for participation. Following confirmation of eligibility, the physicians will obtain informed consent prior to surgery at the planned preoperative visit. Last year, the combined surgical volume of these cases at our three clinics was 532 subjects; thus, we anticipate we will be able to easily recruit the proposed sample size in twelve months. **ENROLLMENT AND BASELINE VISIT:** Patients who are being discharged home with an indwelling catheter following pelvic reconstructive surgery will be enrolled into the study. With regards to outpatient surgery (such as a suburethral sling), this will occur within a few hours after surgery for patients who fail their trial of void. Following inpatient surgery (such as sacrocolpopexy, uterosacral or sacrospinous ligament fixation, or colpocleisis), patients who are being discharged from the hospital with an indwelling catheter will be enrolled into the study. As per standard of care, all subjects will be scheduled for an office visit for catheter removal 24 to 72 hours after placement of the indwelling catheter per surgeon preference. Demographic information will be collected from the patients medical record (age, menopausal status, concurrent estrogen use, ethnicity, level of education, medical comorbidities, history of recurrent UTIs, and duration of hospitalization). Data regarding the patients surgical intervention (procedure type, surgical complications, operative time) will be collected from the operative record. At the time of catheter removal, subjects will be randomized to either methenamine hippurate or fluoroquinolones, using sealed, opaque, sequentially numbered envelopes. All patients, and all physicians and nurses directly involved in patient calls and clinical interaction, will be masked to treatment allocation. Only the nurses involved in catheter removal, but not decisions on the primary outcome, will open the envelope, and distribute the allocated medication to the patient, who will take one dose at the office. A 24-hour course of fluoroquinolones, as per AUA guidelines, are the first-line antibiotics for catheter removal, and will be one of the active arms of the study. Due to differences of office practice and formulary availability, the fluoroquinolone of choice at each site will be different; this is clinically relevant as different urology practices across the country use different fluoroquinolones for prophylaxis. At HUP and Radnor, the 24 hour course of fluoroquinolone used will be one dose of 500 mg of levofloxacin, as per office practice and formulary availability. At the other sites (Pennsylvania Hospital, Chestnut Hill Hospital), the 24 hour course of fluoroquinolone as per office practice will be two doses of 500 mg of ciprofloxacin, 12 hours apart. Methenamine hippurate will be given as two doses of 1g of methenamine hippurate, taken 12 hours apart. The patient will not be told which

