
medication they are taking. The methenamine, ciprofloxacin, and levofloxacin used in this study are all similar in shape, although not in color. Following catheter removal one to two hours after the first dose of medication, patients will be given a white vial or bag with the second dose of medication (if given methenamine or ciprofloxacin) and will be instructed to take second dose of the study medication at home about 12 hour later. As part of standard of care, nurses perform void trials per practice guidelines by backfilling the bladder with 300 cc normal saline, removing the catheter, and prompting the patient to void immediately. If a patient fails her trial of void, majority of the patients at our site are taught intermittent self-catheterization. If an indwelling catheter is replaced, the allocated treatment (drug or placebo) will be re-administered at repeat trial of void/repeat catheter withdrawal. No further drug will be given if the patient performs intermittent self-catheterization after the failed trial of void. FOLLOW UP VISITS: Three weekly follow-up calls and one postoperative visit are planned. It is standard of care of our clinical practices in the office for a clinical urogynecology nurses to routinely contact patients post-surgery to ask about any symptoms or complications from the procedures they underwent. In this study, per routine office practice, urogynecology nurses will call study participants once a week for the first three weeks following surgery. As per routine, using a structured form, patients will be asked about symptoms of UTI, any treatment for UTI, any urine laboratory testing, visits, and treatment for suspected UTI from other providers other than the urogynecology clinic (e.g. ER, primary care doctor), treatment of complications secondary to UTI (such as pyelonephritis and sepsis), and any additional use of antibiotic for infections other than UTI. Questions related solely to the study medication will include compliance with medications given, and side effects within 24 hours of taking medication. At any time during the study, as per standard of care of all urogynecology patients, patients who feel that they may have UTIs will be encouraged to call the urogynecology clinical nurses or the on-call physician with their symptoms. These encounters, any testing, and any empiric treatment are documented in the electronic medical system. If the diagnosis of UTI is unclear at any time, per standard of care, the patient will be asked to come into the office for physical examination and further diagnostic testing. If patients are suspected of having UTI, treatment for UTI will be initiated. As per routine office care for treatment of UTI, if possible, all patients will be asked to give a specimen for urinalysis and urine culture prior to beginning empiric treatment. Four to eight weeks following surgery, as per standard of care, patients will return to the office for a routine post-operative assessment with the investigating physicians. The patients will undergo routine post-operative physical examination and answer the above questions. Any methenamine or ciprofloxacin that has not been taken as instructed will be returned at this time. At their post-operative visit, the patient will be asked if they were aware of which medication they were taking to assess blinding.

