### **Data and Safety Monitoring**

This study contains low risks, as both of these medications are already used in clinical practice for prophylaxis of urinary tract infections. Study progress and safety will be reviewed by the PI. Review of the rate of subject accrual, adherence to inclusion/exclusion criteria will occur to assure that participants meet the eligibility criteria. There will be ongoing collection of data on adverse events and compliance to the treatment protocol throughout the study by research staff.

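### At the single-dose levofloxacin sites, asking about the second dose on the weekly calls can reveal the arm to callers the protocol describes as masked

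*Combined protocol and SAP*

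**What the plan says.** Four parts of the combined protocol and SAP bear on this.

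- **Masking (Procedures):** "All patients, and all physicians and nurses directly involved in patient calls and clinical interaction, will be masked to treatment allocation". Only the catheter-removal nurse opens the envelope, and that nurse takes no part in decisions on the primary outcome.
- **Regimens (Procedures):** methenamine is two doses at every site. At HUP and Radnor "the 24 hour course of fluoroquinolone used will be one dose of 500 mg of levofloxacin"; at Pennsylvania Hospital and Chestnut Hill the fluoroquinolone is two doses of ciprofloxacin. Accrual names HUP alone for levofloxacin. For the dose taken at home, "patients will be given a white vial or bag with the second dose of medication (if given methenamine or ciprofloxacin"). No dummy second dose is described for levofloxacin patients.
- **Calls:** Secondary outcome variable(s) says "investigators will also ask patients during the weekly routine post-operative call and routine post-operative visits about their compliance with the second dose of medication". Procedures has urogynecology nurses call weekly for three weeks, asking on the same call about UTI symptoms, UTI treatment, compliance and side effects.
- **Primary outcome (Primary outcome variable(s)):** antibiotic treatment for suspected UTI within three weeks of surgery, based on "development of 2 or more of the following symptoms, in the absence of vaginal symptoms"; "a positive urine culture will not be required as part of the primary outcome".

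**The concern.** At a levofloxacin site, whether a patient has a second dose identifies her arm. The plan prompts for that fact on the calls that gather primary outcome information. One section has investigators asking and another has nurses calling; the masking statement covers both. The urogynecology nurses are also among those whom patients are told to phone with symptoms, so an informed caller can be involved when treatment is decided.

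With a culture-confirmed endpoint this would matter less. Here the event is a treatment decision prompted by reported symptoms. If knowledge of the arm changes whether a patient is treated within the three weeks, the recorded rate in that arm changes. Under-calling in the methenamine arm would favour a false finding of non-inferiority; over-calling would cost power. The blinding check at the post-operative visit asks patients only, so unmasking of callers would go unseen.

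**Working it through.** **What the answer reveals, by site**

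| Sites (Procedures) | Methenamine | Fluoroquinolone | Does the second-dose answer separate the arms? |
|---|---|---|---|
| HUP, Radnor | two doses, second at home | one dose, none at home | Yes, completely if reported accurately |
| Pennsylvania Hospital, Chestnut Hill | two doses, second at home | two doses, second at home | No |

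Misreporting blurs this only a little. Assume 1:1 allocation, that a share e of methenamine patients wrongly say no second dose was issued, and that all levofloxacin patients say none was. Then P(fluoroquinolone | none reported) = 1/(1 + e): 100% at e = 0, 95% at 5%, 91% at 10% and 83% at 20%, against 50% before the question.

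**Does anything else in the plan cure it?** The protocol description and the re-administration text mention placebo, but both arms are active and no placebo second dose is described. The application form answers yes to over-encapsulating or compounding, but Procedures says the pills differ in colour, and encapsulation would not supply a missing dose.

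**The plan's own sample size (Accrual)**

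Inputs: 22% in both arms, margin 15 points, one-sided alpha 0.025, power 80%.

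n = (1.960 + 0.842)² × 2 × 0.22 × 0.78 / 0.15² = 119.7, so 120 per arm and 240 in total. This reproduces the stated figure.

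**Illustration of size**

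The documents do not give the inputs below, so these results do not establish an effect. Assumed:

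- levofloxacin sites hold 20–50% of patients;
- an informed caller shifts the recorded methenamine rate there by 10–20% relative;
- a fraction f of treatment decisions passes through an informed caller. The rest bypass one, because they are made before disclosure or by an on-call physician, emergency room or primary care doctor;
- the test is a two-sided 95% Wald interval for the risk difference, with success if the upper limit is below 15 points. The Analysis Plan specifies only a relative risk.

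Let k = share × shift × f. Exact binomial probabilities with 120 per arm and a control rate of 22% give false non-inferiority at a recorded methenamine rate of 37% × (1 − k), and power at 22% × (1 + k).

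| f | k | False non-inferiority (under-calling) | Power (over-calling) |
|---|---|---|---|
| 0 (no leak or no bias) | 0 | 2.5% | 80% |
| 0.25 | 0.005–0.025 | 2.7–3.6% | 80–77% |
| 0.5 | 0.01–0.05 | 2.9–5.1% | 79–73% |
| 1 (upper bound) | 0.02–0.10 | 3.3–9.5% | 78–66% |

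The last row is a bound only, since Procedures lets patients reach the on-call physician and expects some to be treated elsewhere. With a Newcombe interval the f = 0.5 row becomes 3.1–5.4% and 79–74%.

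**Break-even (Wald).** False non-inferiority reaches 5% at k = 0.0492: 37 × 0.0492 = 1.82 points, and 0.0182 × 120 = 2.2 patients. At f = 0.5 that requires informed callers to under-call by 0.0492/(0.5 × share), which is 49%, 33% or 20% for shares of 0.2, 0.3 and 0.5. Power falls to about 75% at k = 0.04: 22 × 0.04 = 0.88 points, about 1.1 patients of 120.

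**The case against.** The explicit reference to a second dose stands in one place. Procedures words the item only as compliance with the medication given, which a levofloxacin patient can answer without revealing anything. The second-dose wording may date from a ciprofloxacin-only comparator, under which it is harmless: the compliance aim in Overall objectives and the costing text both name ciprofloxacin. The call form is not in the documents. Resources necessary for human research protection says the nurses are informed of the protocol, not that each learns her site's regimens. So an operating leak is not proven. That stands, but the current text still prompts the disclosure while claiming masking, and the sections need to agree.

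The safeguards are real: the two-symptom rule, a structured form, examination when the diagnosis is unclear, a urine specimen requested before treatment where possible, an envelope-opening nurse kept out of outcome decisions, and culture-positive UTI as a secondary outcome. They narrow what a caller can change; they do not restore masking.

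Timing also limits the effect. UTIs treated before the first call cannot be influenced by its compliance answer, and if the form asks the UTI items first, the week 1 answers are safe too. The calls in weeks 2 and 3, and later calls from patients, are not. Earlier or later treatment within the three weeks does not alter a binary outcome; only whether treatment occurs does.

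The count of about two patients also sounds small beside the 20–49% under-calling it requires when half of decisions bypass an informed caller. That is a fair caution, and the conclusion does not rest on these figures.

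**Conclusion.** The concern holds and should be fixed. Read together, the masking, dispensing and call sections let a caller who knows the regimens identify the arm at the single-dose sites, and nothing elsewhere in the plan prevents it. Confidence is high for this contradiction. Whether callers do learn the arm, and whether that changes treatment, is not known; any bias may be nil, and its direction cannot be stated. The error-rate and power ranges rest on assumed values for site share, bias, bypass fraction and interval method. The ciprofloxacin sites are unaffected by dose count. The case for acting is that the masking claim conflicts with the plan's own procedures, the outcome is open to judgement, and the remedy costs little.

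**What to change.** 1. **Take the compliance item off the outcome calls in weeks 1 to 3.** Ask it at the post-operative visit at four to eight weeks, where it is already asked and unused tablets come back, after the UTI items are recorded. Data and Safety Monitoring says "There will be ongoing collection of data on adverse events and compliance to the treatment protocol throughout the study by research staff". If that is kept, assign it to existing research staff with no role in UTI calls or treatment decisions, and bar them from passing the answer on. The research nurses also help with post-operative care, so this separation must be written down. Keep the side-effect questions in the calls, tied to 24 hours after the last study medication taken and without asking how many doses. This preserves the stated window, "that may occur within 24 hours of the administration of the last dose of methenamine or antibiotic", for one-dose and two-dose patients alike. Align Secondary outcome variable(s), Procedures and Data and Safety Monitoring with the change.
2. **Correct the masking statement.** Say who is masked at which sites, and that masking is incomplete at single-dose sites because patients may volunteer the information. Reconcile Accrual with Procedures on which sites use levofloxacin.

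**Cost.** The first change moves one item between existing forms or to existing staff. Its downside is later recall for the compliance aim, partly offset by returned methenamine and ciprofloxacin and avoided if separate staff ask early. Adherence should not suffer. On the plan's timings the second dose is due by about 72 + 12 = 84 hours, and the side-effect window closes by about 84 + 24 = 108 hours (4.5 days). Both precede a first call at about day 7 (assumed), provided the catheter is placed at surgery and not replaced. The second change is wording only.

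**Optional, outside the core fix:** an identical take-home package holding an inert look-alike where the allocated regimen has no second dose, with no active regimen altered. It would cost more because the pills differ in colour; the documents give no price.

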**Analysis Plan**

Categorical variables will be analyzed using chi-squared or Fishers exact test and parametric or non-parametric t-tests for continuous variables. Bivariable analysis will be used to determine variables (risk factors) that are independently associated with post-operative UTI. Duration of catheterization between groups will be compared using the Mann-Whitney test to compare difference in medians. The primary outcome will be the rate of clinically suspected UTI requiring treatment within the first three weeks following surgery. Comparison with fluoroquinolones will be performed using relative risk ratio. Analysis will be performed by intention to treat. If imbalances in baseline demographics are identified, multivariate analyses for post-operative UTI will be performed to control the inequality. Cost-effectiveness analysis will be performed by monetizing the collected resource utilization data in each treatment arm, including use of intervention resources, UTI treatment resources, as well as primary and secondary care resources. Incremental cost-effectiveness ratios will be calculated to compare difference in costs between prophylaxis with methenamine and prophylaxis with fluoroquinolones to the difference in effect on the incidence of post-operative UTI. Prevalence of adverse effects will be measured as

percentages. Rate of urine cultures performed by patients treated for symptomatic UTI, as well as the rate of culture-positive UTI will be noted; comparison with fluoroquinolones will be performed using relative risk ratio, with analysis by intention to treat. Positive cultures will be analyzed for percentage of uropathogen type, type of uropathogen showing resistance, and overall percentage of cultures showing resistance.

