
minimal. Any patients with any side effects will be told to discontinue use of the medications and be evaluated by a physician, and any serious adverse events will be reported to the IRB. There are no psychological, social, economic, monetary, or legal risks to this study. Loss of confidentiality: Any study in which personal health information (PHI) is collected has the potential risk of loss of confidentiality. However, extensive efforts will be made to ensure and maintain security of PHI and maintain participant confidentiality. Patients will be identified and screened by physician investigators at each site involved in patient care in their offices. The patient will be brought into a private room before discussing the study and enrollment with the patient in the privacy of a private room. During the study, interactions patient will involve routine post-operative care by the physician investigators and urogynecologic nurses, which is conducted in physicians' offices. It will also involve routine post-operative telephone calls, done in a private manner in the office setting, in the usual manner. Data from patients will be recorded on data collection forms, which will be associated with a Subject ID number only. The patient name, medical record numbers, or other identifiers will not be present on the data collection forms themselves. The Participant ID number will be composed by the sequential ordering of participants. At each site, a log book will be kept in for data management purposes to match Subject ID number with patient medical record numbers if chart review is needed for missing data. This will also be maintained in a secure and locked filing system at all times. Any additional source documentation that may associate the patient and PHI to data (such as consent forms) will also be kept in a secure and locked filing system at all times. Additionally, any data collection forms will also be kept in a separate secure and locked filing system at all times. One year after the study has been completed, any forms with patient identifiers (such as logs and consents) will be destroyed. At the University of Pennsylvania, the participant will be logged in the Excel spread sheet using their assigned Subject ID number. The Excel spreadsheet form will be stored in a password-secured file and a physical backup copy of this file will be made at the end of every other week and the copy stored in a separate, secure area/filing system. [1] Methenamine. In: Micromedex 2.0. Martindale - The Complete Drug Reference. Ann Arbor, MI: Truven Health Analytics. [updated 8/20/2010; accessed 2/21/14]. <http://www.micromedexsolutions.com/micromedex2/librarian/>. [2] Ciprofloxacin. In: Micromedex 2.0. Martindale - The Complete Drug Reference. Ann Arbor, MI: Truven Health Analytics. [updated 8/20/2010; accessed 2/21/14]. <http://www.micromedexsolutions.com/micromedex2/librarian/>. [3] Levofloxacin. In: Micromedex 2.0. Martindale - The Complete Drug Reference. Ann Arbor, MI: Truven Health Analytics. [updated 8/20/2010; accessed 2/21/14]. <http://www.micromedexsolutions.com/micromedex2/librarian/>.

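### The cost analysis promises to count physician and emergency care, but the follow-up form does not ask about care for study-drug side effects, and the ratio has no stated common time window

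*Combined protocol and SAP*

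**What the plan says.** **What is to be costed.** Secondary outcome variable(s) states: "We plan to perform a cost-effectiveness analysis from a societal perspective, which will be expressed as incremental cost per UTI prevented". The services to be counted are broad: "Direct medical service standard of care use (such as number and types of physician visits, hospital admissions lengths, emergency transport and emergency room visits". The examples of direct medical cost are narrower: "such as antibiotic treatment of UTI, prophylaxis with methenamine or ciprofloxacin, urine laboratory tests, or treatment of complications like pyelonephritis". The Analysis Plan lists "use of intervention resources, UTI treatment resources, as well as primary and secondary care resources" on the cost side and sets the cost difference against the "difference in effect on the incidence of post-operative UTI".

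**What side effects lead to.** Potential Study Risks says: "Any patients with any side effects will be told to discontinue use of the medications and be evaluated by a physician".

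**What is asked.** The structured form described under Procedures covers UTI symptoms and treatment, urine tests, visits and treatment for suspected UTI at other providers, treatment of UTI complications, and antibiotics for other infections. For the study drug: "Questions related solely to the study medication will include compliance with medications given, and side effects within 24 hours of taking medication".

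**When it is asked.** Calls are weekly for three weeks. After that, "Four to eight weeks following surgery, as per standard of care, patients will return to the office", where the same questions are put again. Study duration places this visit at six weeks. The primary outcome counts UTIs treated within three weeks of surgery.

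**The concern.** Cost-effectiveness is in the trial's title and is the first secondary aim. The protocol argues for methenamine partly on fewer adverse effects and lower cost. The protocol's own instruction generates physician evaluations for side effects, and these belong to the cost categories it promises to count. The form records that a side effect occurred but not the visit, test or treatment that followed. If that care differs between arms, the cost difference is wrong by the amount left out. Care that is not asked about during follow-up may not be recoverable later, especially when it was given outside the health system.

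The second issue is the time window. Data are collected to three weeks by telephone and again at a later visit whose timing varies. No section says over what period costs and UTIs enter the ratio, so the analyst could choose after seeing the data.

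**Working it through.** The plan states no figure for the cost-effectiveness ratio, so there is none to reproduce. The sample size plays no part in this point.

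**A. Promised cost against planned collection**

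| Item | Promised as a cost? | Asked on the form? |
|---|---|---|
| Visits and treatment for suspected UTI | Yes | Yes |
| Treatment of UTI complications | Yes | Yes |
| Side effect occurred | Not a cost in itself | Yes, within 24 hours |
| Visit, test or treatment for a side effect | Yes, within physician visits, emergency visits, and primary and secondary care | No question listed |

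**B. Size of the omission**

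Inputs from Potential Study Risks: nausea 3.5% or less (methenamine), 2.5% to 4% (ciprofloxacin), 7% (levofloxacin). Assumed: $100 per evaluation and every case evaluated.

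Omitted difference per woman = (fluoroquinolone rate − methenamine rate) × share evaluated × cost per evaluation.

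- Ciprofloxacin, upper rates: (0.04 − 0.035) × 1 × $100 = $0.50
- Levofloxacin: (0.07 − 0.035) × 1 × $100 = $3.50
- Ciprofloxacin at its lower rate: (0.025 − 0.035) × 1 × $100 = −$1.00, so the sign is not certain for that drug

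With 25% to 100% evaluated and $75 to $600 per case (both assumed), the upper rates give from 0.005 × 0.25 × $75 = $0.09 to 0.035 × 1 × $600 = $21.00 per woman. If the arms differ by 3 points in UTI (assumed), dividing by 0.03 moves the ratio by about $3 to $700 per UTI.

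For scale, Background gives $2 per methenamine pill and $3 to $17 per pill for commonly used antibiotics (not ciprofloxacin alone). Assume one pill per dose. Two methenamine doses cost $4.

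- Against two antibiotic doses ($6 to $34), the difference is $4 − $6 = −$2 to $4 − $34 = −$30.
- Against a single levofloxacin dose ($3 to $17), it is $4 − $3 = +$1 to $4 − $17 = −$13.

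**C. Does a window mismatch shift the ratio?**

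Illustration: $600 per UTI (Background), drug cost $4 v $34, and three-week UTI 25% (assumed) v 22% (Accrual, for antibiotic prophylaxis). With both sides at three weeks, the cost difference is −$30 + $600 × 0.03 = −$12, or $12 / 0.03 = $400 saved per extra UTI. Now let costs run late. All late rates below are assumed.

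| Late UTI, methenamine v fluoroquinolone | Cost difference | Costs late, UTIs to three weeks | Both late |
|---|---|---|---|
| 3% v 3% | −$30 + $600 × 0.03 = −$12 | $400 | $400 |
| 2% v 4% | −$30 + $600 × 0.01 = −$24 | $24 / 0.03 = $800 | $24 / 0.01 = $2,400 |
| 4% v 2% | −$30 + $600 × 0.05 = $0 | $0 | $0 |

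A mismatch moves the expected cost difference only if late UTIs differ between arms, and it can do so in either direction. With equal late risk p it adds noise. At 120 per arm the standard error is $600 × √(2p(1 − p)/120), which is about $8 at p = 1% and $17 at p = 5%.

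**The case against.** **The cost categories are already wide enough.** Both lists under Secondary outcome variable(s) are examples, and the services list is not limited to UTI. This is correct, so side-effect care is not excluded from the costs. But the plan then promises more than the form is shown to collect.

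**The care would be found elsewhere.** The section on resources for human research protection gives women with drug reactions 24-hour access to the on-call physician or the investigators' offices. Data and Safety Monitoring plans ongoing adverse-event collection. Much of this care may therefore fall within the study's own practices. Neither section says that it will be extracted for costing. The sentence in Procedures on electronic documentation concerns women who think they have a UTI. Outside care remains uncovered.

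**The count can be imputed.** If every side effect leads to one evaluation, the recorded side effects approximate the number of evaluations. This stands for the basic visit. It does not supply tests, treatment or emergency care, it assumes that every woman follows the advice, and the plan does not propose it.

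**The form's list is not exhaustive.** It says what the questions will include, and its mention of visits could be read more widely than suspected UTI. If so, stating it costs almost nothing.

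**The windows.** A reader might infer that costs run to four to eight weeks while UTIs in the ratio stop at three. The documents do not say this. The three-week limit belongs to the primary outcome, the UTI incidence in the ratio carries no limit, and the last visit repeats the UTI questions along with the resource questions. A late UTI can be counted on both sides. What stands is that the window is unstated.

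**Conclusion.** The side-effect point holds. Following the plan as written, care for study-drug reactions would not be reliably captured, although the plan promises to cost such care and the protocol itself generates it. The cost difference could be biased, probably by understating fluoroquinolone cost if the quoted rates apply. The size is about $0.50 to $3.50 per woman at the upper nausea rates and an assumed $100. It would be larger if care costs more or other side effects are counted. It is small against much of the possible drug-price difference but comparable with its lower end. The quoted rates may not carry over to these short courses, for which the protocol itself expects less risk.

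The stronger conclusion, that the ratio is biased, is not shown. It needs a difference between arms in side-effect care or in late UTIs, and the documents establish neither. On timing, the supportable statement is that no common window is given and that the two stated times of the post-operative visit disagree. This concerns one secondary outcome; neither the primary analysis nor the sample size changes.

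**What to change.** 1. **Procedures:** add one question to the existing calls and visit on any visit, test or treatment for a suspected study-drug side effect, including care from outside providers.
2. **Secondary outcome variable(s) and Analysis Plan:** name this care among the costed items.
3. **Analysis Plan, as a secondary clarification:** state one common window for UTIs and costs. For example, take UTIs with onset within three weeks of surgery and follow all costs of those episodes to the post-operative visit. Show later episodes, counted on both sides, as a sensitivity analysis. A plain cut of all resource use at three weeks would drop the later cost of UTIs that began before then.
4. **Study duration and Procedures:** reconcile the two statements of when the post-operative visit takes place.

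The cost is one extra form question and slightly more analysis work. Treatment, number of contacts and sample size are unaffected.
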